7.5. Medication

Prior and concomitant medications will be coded using the World Health Organization (WHO) Drug B2 Format, Mar 1st, 2017 version.

Except for Prior OAB medication, the number and percentage of patients taking prior medications and concomitant medications will be summarized overall by ATC (Anatomical Therapeutic Chemical) Levels 2 and 4, in separate tables, for all patients in the SAF. Prior OAB medications will be summarized by ATC Levels 2, 4 and Preferred Term in the SAF.

Prior medications, OAB medication and concomitant medications will be listed for all patients in the SAF

7.5.1. Prior Medication

Prior medications will be defined as medications documented on the Prior and Concomitant Medications eCRF as having stopped prior to the Run-in Visit.

7.5.2. Concomitant Medication

Concomitant medications will be summarized separately for the Run-in Period and Double-Blind Period. Concomitant medications will be defined as taken during the Run-in Period if medications were started on or after the first dose of single-blind medication but prior to the first dose of the double-blind medication, or started prior to the first dose of the single-blind medication and were continuing to be taken during the Run-in Period. Concomitant medications will be defined as taken during the double-blind period if medications were started on or after the first dose of double-blind medication but prior to the last dose of the double-blind medication, or started prior to double-blind medication and were ongoing during the Double-Blind Period. Partial medication start dates will be imputed as detailed in [Section 6.4](#).

7.5.3. Other Therapies

Prior OAB medication will be recorded at screening visit. The following criterion will be used for selecting prior OAB medication:

Table 7.5.3: OAB Medication Selection

Class	Variable Selected	Selection
Anticholinergics	Preferred Term	darifenacin, fesoterodine, festoterodine fumarate hyoscyamine, oxybutynin, oxybutynin hydrochloride, propantheline, solifenacin, solifenacin succinate, tolterodine, tolterodine l-tartrate, trospium, and trospium chloride
Beta-3 adrenergic agonists	Preferred Term	Mirabegron, vibegron

8. EFFICACY ANALYSIS

Throughout the trial, patients were required to fill out an event and volume diary. It was intended for the patients to fill out the voiding diary for 7 days prior to the Run-in, Baseline, Week 2, Week 4, Week 8, and Week 12 visits, and to fill out the volume portion of the diary for 1 of the 7 diary days for each visit. Duplicate data recorded by the patient in diary rows with identical values will be not removed.

The definitions of a “Diary Day”, “Complete Diary Day”, and Baseline are given in [Section 6.3](#).

In order for a patient to have an evaluable change from baseline, the patient must have both a complete baseline diary and a post-baseline assessment from any post-baseline value (i.e., Week 2, Week 4, Week 8, or Week 12) for either micturitions for the FAS or UUI for the FAS-I. Change from baseline is defined as the post-baseline assessment minus the baseline assessment.

In general, the Full Analysis Set (FAS) will be used for all non-incontinence efficacy endpoints. The FAS-I will be used for all incontinence efficacy endpoints; these are the endpoints related to urge urinary incontinence (UUI) episodes and total incontinence episodes.

8.1. Co-Primary Endpoint Analysis

8.1.1. CFB in Micturitions at Week 12

In this study, the number of micturitions is defined as the number of times a patient has voided in the toilet as indicated on the Voiding diary. Average daily number of micturitions will be calculated as the total number of micturitions that occur on a Complete Diary Day divided by the number of Complete Diary Days in a voiding diary, consisting of at least 4 complete diary days.

The FAS will be the analysis population for the micturition endpoint.

8.1.1.1. Primary Analysis

A mixed model for repeated measures (MMRM) with restricted maximum likelihood estimation will be used as the primary analysis model for change from baseline in average number of daily micturitions at Week 12. This model includes data from Week 2, Week 4, Week 8 and Week 12 and corrects for data that is missing at random (MAR), accounting for the fact that measurements taken on the same patient over time tend to be correlated, by using all available information on patients within the same covariate set to derive an

estimate of the treatment effect for a MAR-free population. No imputation of missing data is required for this analysis. The analysis model will include terms for treatment, visit, OAB Type (Wet vs Dry), Sex (Female vs Male), Region (US vs non-US), baseline score, and interaction of visit by treatment.

Primary inference will be drawn from the treatment difference between vibegron and placebo at Week 12. The comparisons between tolterodine and placebo will be reported with nominal p-values. The standard error and 95% CI for the differences will also be presented with the corresponding p-values. Additionally, estimates of least-squares means, standard errors, and 95% CIs will be presented for each treatment group (placebo, vibegron and tolterodine). The table output will also include treatment group estimates and treatment differences between vibegron and placebo, and tolterodine and placebo at Weeks 2, 4, and 8 from this model.

An unstructured covariance matrix will be used to model the correlation among repeated measurements. The Kenward-Roger adjustment will be used with restricted (or residual) maximum likelihood (REML) to make statistical inference. If the unstructured covariance model fails to converge with the default Newton-Raphson algorithm, the Fisher scoring algorithm will be used to provide initial values of the covariance parameters. In the rare event that none of the above methods yield convergence, the following structures will be investigated: heterogeneous Toeplitz, Toeplitz, heterogeneous First-Order Autoregressive [AR (1)], heterogeneous compound symmetry (HCS), and compound symmetry (CS). The covariance structure converging to the best fit, as determined by Akaike's information criterion (AIC), will be used.

An example of the SAS code for the base procedure is given below:

```
proc mixed data = datain method = reml ;
  class TRTP AVISITN USUBJID OABTYPE SEX REGION ;
  model CHG = TRTP AVISITN OABTYPE SEX REGION BASE TRTP*AVISITN
    / ddfm=KR solution chisq ;
  REPEATED AVISITN / subject=USUBJID type=UN r rcorr ;
  LSMEANS TRTP*AVISITN / pdiff=all cl alpha=0.05 ;
run ;
```

Where TRTP is the planned treatment, AVISITN is the visit number, USUBJID is the unique patient identifier, OABTYPE indicates if the patient is Dry or Wet, SEX is female or male, REGION indicates if the patient is in the United States or in the non-US countries and BASE indicates baseline value.

[figure not shown]
Model assumptions will be assessed through inspection of residual plots and normal probability plots. Should gross violations of the assumptions occur, the change from baseline in average daily micturitions will be transformed prior to the modeling.

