3.8. Determination of Sample Size

Approximately 1,400 patients will be randomized in a 5:5:4 ratio to receive one of the following Study Treatments:

- Vibegron 75 mg + placebo to match tolterodine ER 4 mg;
- Placebo to match vibegron 75 mg + placebo to match tolterodine ER 4 mg; or
- Tolterodine ER 4 mg + placebo to match vibegron 75 mg.

Approximately 500 patients will be assigned to the vibegron and placebo treatment groups, and approximately 400 patients will be assigned to the tolterodine treatment group. Assuming that a total of 10% of patients will discontinue prior to Week 12 (for any reason), there will be approximately 450 evaluable patients in the vibegron and placebo treatment groups at the end of Week 12. Assuming 75% of the population will have OAB Wet, there will be approximately 337 evaluable patients in the vibegron and placebo treatment groups for the incontinence endpoints. The study has:

- Approximately 98% power to detect a true underlying between-group treatment difference in vibegron vs. placebo of 0.6 in change from baseline in micturitions at a two-sided 0.05 level assuming a variability estimate of 2.20 based on vibegron Study 008 data.
- Approximately 98% power to detect a true underlying between-group treatment difference in vibegron vs. placebo of 0.51 in change from baseline in urge urinary incontinence at a two-sided 0.05 level assuming a variability estimate of 1.68 based on vibegron Study 008 data.

Assuming that these endpoints are uncorrelated, this study has 96% power to reject both co-primary hypotheses at a two-sided 0.05 level. These alternative hypotheses are:

- **Co-Primary Alternative Hypothesis 1:** In patients with OAB, vibegron 75 mg will have a different mean change from baseline (CFB) in the average number of daily micturitions than placebo at Week 12.
- **Co-Primary Alternative Hypothesis 2:** In patients with OAB Wet, vibegron 75 mg will have a different mean CFB in the average number of daily UUI episodes than placebo at Week 12.

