8.1.2.1. Primary Analysis

The primary analysis model for UUI is similar to the micturition model detailed in [Section 8.1.1.1](#) but excluding the term of OAB Type since the UUI endpoint is only collected for OAB Wet patients. More specifically, the primary inference will be drawn from the treatment difference between vibegron and placebo at Week 12. The comparisons between tolterodine and placebo will be reported with nominal p-values. The standard error and 95% CI for the differences will also be presented with the corresponding p-values. Additionally, estimates of least-squares means, standard errors, and 95% CIs will be presented for each treatment group. The table output will also include treatment group estimates and treatment differences between vibegron and placebo, and tolterodine and placebo at Weeks 2, 4, and 8 from this model.

Model assumptions will be assessed through inspection of residual plots and normal probability plots. Should gross violations of the assumptions occur, the change in UUI will be transformed prior to the modeling.

The FAS-I will be the analysis population for the UUI endpoint.

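### The primary MMRM holds the baseline slope constant over Weeks 2 to 12; a baseline-by-visit term would protect Week 12 precision at almost no cost

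*SAP*

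**What the plan says.** SAP 8.1.1.1 specifies an MMRM for change from baseline in daily micturitions: "This model includes data from Week 2, Week 4, Week 8 and Week 12". The fixed effects are treatment, visit, OAB Type, sex, region, "baseline score, and interaction of visit by treatment". The example code matches: "model CHG = TRTP AVISITN OABTYPE SEX REGION BASE TRTP*AVISITN". Treatment is the only term that interacts with visit. For the covariance, "An unstructured covariance matrix will be used to model the correlation among repeated measurements", with REML and Kenward-Roger.

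On the estimand: "Primary inference will be drawn from the treatment difference between vibegron and placebo at Week 12". Section 8.1.2.1 carries the structure to the second co-primary endpoint: "The primary analysis model for UUI is similar to the micturition model detailed in" 8.1.1.1, with OAB Type removed. Sections 8.2.2 (urgency), 8.2.5 (total incontinence), 8.2.7 (volume voided) and 8.3.3 (PGI-Severity and PGI-Control) also refer back to 8.1.1.1. The visible text gives no reason for a constant baseline slope and reports no slopes by visit.

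**The concern.** The treatment effect and the covariance may differ by visit, but the effect of baseline may not. The fitted slope is therefore a weighted average over four visits. If the true slope at Week 12 differs from that average, the part of the Week 12 change that baseline could explain, but the pooled slope does not, stays in the residual and widens the Week 12 standard error.

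Drift is conceivable for these endpoints. UUI counts cannot fall below zero, and SAP 4.2 frames response as proportional reductions of 50%, 75% and 100%. If response were roughly proportional to baseline and grew over time, the slope of change on baseline would steepen from visit to visit. That is an argument from the structure of the endpoint; nothing in the SAP confirms or excludes it.

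Precision at Week 12 is what is at stake, for both co-primary contrasts and for the three key secondary endpoints analysed with the same repeated-measures model. The Coping Score model in 8.2.6 has a single post-baseline visit, so its baseline slope is already specific to Week 12.

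**Working it through.** **1. The plan's own power.** Inputs from SAP 3.8 are 450 evaluable per arm for micturitions ("Approximately 98% power to detect a true underlying between-group treatment difference in vibegron vs. placebo of 0.6", "at a two-sided 0.05 level assuming a variability estimate of 2.20 based on vibegron Study 008 data") and 337 per arm, difference 0.51, SD 1.68 for UUI. With SE = SD × √(2/n) and power = Φ(difference/SE − 1.96):

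- Micturitions: SE = 2.20 × √(2/450) = 0.1467; 0.6/0.1467 = 4.09; power 98.3%.
- UUI: SE = 1.68 × √(2/337) = 0.1294; 0.51/0.1294 = 3.94; power 97.6%.
- Both, uncorrelated: 0.983 × 0.976 = 96.0%.

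The stated 98%, 98% and 96% reproduce.

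**2. What a common slope costs.** Let β12 be the true Week 12 slope, b the pooled slope and SDb the baseline SD. In large samples with complete data, the Week 12 residual variance is SD² + (β12 − b)² × SDb². The proportional inflation relative to a model with BASE*AVISITN is therefore (β12 − b)² × SDb² / SD².

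**3. Assumptions.** The SAP supplies none of these.

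- Total slope drift D from Week 2 to Week 12: 0, 0.10, 0.20 or 0.30.
- Baseline SD: 2 to 4 for micturitions, 1.5 to 3.5 for UUI.
- Visit correlations: compound symmetry 0.6 or 0.8, or first-order autoregressive 0.7.
- Gap β12 − b = c × D, with c depending on path and correlation. The paths examined give c from 0.45 to 0.50; c = 0.50 corresponds to equal steps between visits.
- The stated SDs 2.20 and 1.68 are taken as residual SDs of the by-visit model.

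Example: micturitions, D = 0.30, SDb = 4, c = 0.45. The gap is 0.135, and 0.135² × 16 / 4.84 = 6.0%. UUI at D = 0.30, SDb = 3.5, c = 0.50 gives 0.15² × 12.25 / 2.8224 = 9.8%.

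| Drift D | Micturitions, Week 12 variance | UUI, Week 12 variance |
|---|---|---|
| 0 | 0% | 0% |
| 0.10 | 0.2-0.8% | 0.2-1.1% |
| 0.20 | 0.7-3.3% | 0.6-4.3% |
| 0.30 | 1.5-7.4% | 1.4-9.8% |

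Each range runs from the smallest baseline SD with c = 0.45 to the largest with c = 0.50. The inflation scales with c². A path that levels off early shrinks it. One proportional to elapsed weeks gives c = 0.55 under compound symmetry and multiplies the c = 0.50 figures by (0.55/0.50)² = 1.21.

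**4. Power.** At D = 0.10 with mid-range baseline SDs, joint power is about 95.9%. At D = 0.30 with the largest baseline SDs, c = 0.50 gives 0.9765 × 0.9642 = 94.2%; autoregressive 0.7, with c about 0.48, gives 0.9772 × 0.9653 = 94.3%.

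**5. Simulation check.** Micturition MMRM, arms of 500/500/400, four visits, unstructured covariance, about 10% dropout missing at random, baseline SD 3, 400 trials per scenario, true difference −0.6:

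| Drift | Model SE, common slope | Model SE, by visit | Mean estimate, common / by visit |
|---|---|---|---|
| 0 | 0.1427 | 0.1427 | −0.605 / −0.605 |
| 0.10 | 0.1429 | 0.1426 | −0.602 / −0.601 |
| 0.20 | 0.1436 | 0.1422 | −0.598 / −0.598 |

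At drift 0.20 the variance ratio is (0.1436/0.1422)² = 1.020. The formula gives 1.5-1.9% at this baseline SD, so the two agree.

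**The case against.** The strongest reply is that this is a modelling preference. Text and code agree, the model is fully specified, and an unstructured covariance with Kenward-Roger is sound. The loss exists only if the slope drifts, and the SAP offers no data on that. The larger figures come from a corner of the assumed range. SAP 3.8 also does not say which model produced 2.20 and 1.68, so any loss may already sit inside the stated power. All of this stands, and it limits the point to an optional improvement. It does not remove the point, because the restriction buys almost nothing: three parameters are trivial with about 1,400 patients.

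Three stronger readings are tempting and unsupported.

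- A reader might infer that the plan certainly gives up precision. With equal slopes the simulated standard error is 0.1427 with or without the term.
- A reader might infer that the Week 12 contrast is biased, or that handling of dropouts is compromised. Randomization protects the contrast, and the simulation with missing-at-random dropout gave means between −0.598 and −0.605 under both models. The unstructured covariance absorbs the added residual variance, so type I error is not at stake. Details of the imputation-based sensitivity analyses are not visible and cannot be judged either way.
- A reader might infer that the trial is underpowered. Even with D = 0.30 and the largest baseline SDs, joint power on the paths examined stays about 94%.

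**Conclusion.** The point holds as a low-cost improvement and not as an error in the plan. One baseline slope is imposed on four visits while inference is at Week 12 only. If the slope changes over visits, some Week 12 precision may be lost: about 0.1-1% of variance at a drift of 0.10, about 0.5-4% at 0.20, and up to 7-10% only at 0.30 with a large baseline SD. With no drift nothing is lost. These sizes depend on the assumed drift, path, baseline SDs and visit correlations, none of which the SAP reports. Validity does not depend on the change, and no conclusion is likely to turn on it.

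**What to change.** Before unblinding, add the baseline-by-visit interaction to the list of model terms in SAP 8.1.1.1 and BASE*AVISITN to the MODEL statement. State that it carries through the MMRMs that refer to that section: UUI (8.1.2.1), urgency (8.2.2), total incontinence (8.2.5), volume voided (8.2.7) and the PGI items (8.3.3). The subgroup models in 8.1.4 spell out their own terms and should be kept aligned.

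The cost is three fixed-effect parameters per model with four post-baseline visits, and two for the PGI items, which have three (Weeks 4, 8 and 12). There is essentially no loss of precision if slopes are constant. The term should be pre-specified, since adding it after unblinding would be open to the charge of a data-driven choice. If the sponsor prefers a single slope, one sentence giving the reason would be enough.

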2.2. Timings of Analyses

The primary analysis of efficacy and the analysis of safety and PK are planned after all patients complete the final study visit or terminate early from the study. No interim analyses will be performed and no Data Safety Monitoring Board has been set-up for this study. This SAP details these analyses and has been finalized prior to unblinding of the study.

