3.9. Treatment Assignment and Blinding

Randomization will occur centrally using an interactive voice or web response system (IxRS) using central, stratified randomization. There are three treatment arms to which patients will be randomized in a 5:5:4 ratio:

- Vibegron 75 mg + placebo to match tolterodine ER 4 mg
- Placebo to match vibegron 75 mg + placebo to match tolterodine ER 4 mg
- Tolterodine ER 4 mg + placebo to match vibegron 75 mg

Randomization will be stratified based on the investigator-determined baseline categorization of OAB, referred to as OAB Type: Wet or Dry (as defined in the protocol inclusion and exclusion criteria), and Sex (Female vs. Male).

Enrollment will be capped based on OAB Dry criteria and sex as follows:

- Up to 25% of the patients enrolled may meet OAB Dry criteria.
- Up to 15% of the patient enrolled may be male.

A double-blind/masking technique will be used: vibegron and its matching placebo and tolterodine ER and its matching placebo will be packaged identically so that treatment blind/masking is maintained. The patient, the Investigator, and Sponsor personnel or delegate(s) who are involved in the treatment or clinical evaluation of the patients will not be aware of the treatment group assignments.

At the end of the study (including the 28-day Follow-up Period), the official, final database will be frozen and unblinded after medical/scientific review has been performed, and data have been declared final and complete. The Sponsor and [REDACTED] as designated representative will be granted access to the unblinded database in order to analyze the data. A clinical study report will be prepared after all patients complete the study.

IxRS should be used for emergency unblinding treatment assignment in the event that this is required for patient safety.

In the event that unblinding has occurred, the circumstances around the unblinding (e.g., date and reason) must be documented promptly, and the Sponsor notified as soon as possible. Only the Principal Investigator or delegate and the respective patient's code should be unblinded. Other Site personnel and Sponsor personnel directly associated with the conduct of the study should not be unblinded.

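### Both co-primary change scores are to be transformed if residuals look grossly abnormal, with no transformation named and no raw-scale result kept, although hypotheses and power are stated on the raw scale

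*SAP*

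**What the plan says.** SAP 8.1.1.1 sets an MMRM on the change from baseline in daily micturitions as the primary analysis. The check on it is visual: "Model assumptions will be assessed through inspection of residual plots and normal probability plots". The consequence follows: "Should gross violations of the assumptions occur, the change from baseline in average daily micturitions will be transformed prior to the modeling". SAP 8.1.2.1 repeats the rule for the second co-primary: "Should gross violations of the assumptions occur, the change in UUI will be transformed prior to the modeling".

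The model whose residuals would be inspected contains treatment and treatment by visit: "model CHG = TRTP AVISITN OABTYPE SEX REGION BASE TRTP*AVISITN". On timing, SAP 2.2 states "This SAP details these analyses and has been finalized prior to unblinding of the study". SAP 3.9 says that, once the data are final, the sponsor and its representative "will be granted access to the unblinded database in order to analyze the data".

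The target is set in SAP 3.8. The first alternative hypothesis is that "vibegron 75 mg will have a different mean change from baseline (CFB) in the average number of daily micturitions than placebo at Week 12". Power is given for a difference in "vibegron vs. placebo of 0.6 in change from baseline in micturitions at a two-sided 0.05 level", and for 0.51 in UUI. All of this is on the untransformed scale.

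The covariance fallback in 8.1.1.1 is treated differently: the alternative structures are listed and AIC decides among them.

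**The concern.** The clause is an order, not an option: if the residuals are judged bad enough, the outcome is transformed before the primary model is fitted. What counts as a gross violation is undefined, the transformation is unnamed, nobody is assigned the decision, and nothing says the raw-scale result stays in the report.

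Two things are at stake. First, the primary analysis could end up answering a different question from the one in the hypotheses and the power statement. Second, two competent analysts following the text could report different primary p-values, and the choice might be made when treatment codes are available. The co-primary tests open the whole key secondary sequence. Urgency episodes (8.2.2), total incontinence (8.2.5) and volume voided (8.2.7) refer back to 8.1.1.1 for their analysis, so the clause arguably extends to them too.

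The trigger could plausibly fire for UUI. It is a diary count with a floor at zero, and a patient who reaches zero has a change equal to minus the baseline value.

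**Working it through.** **Step 1: reproduce the stated power on the raw scale.** Inputs from SAP 3.8: 450 per arm, difference 0.6, SD 2.20 (micturitions); 337 per arm, difference 0.51, SD 1.68 (UUI); two-sided 0.05. Formula: power = Φ(δ / (σ√(2/n)) − 1.96).

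- Micturitions: 2.20 × √(2/450) = 0.14667; 0.6 / 0.14667 = 4.091; Φ(2.131) = 0.9835. Stated: 98%.
- UUI: 1.68 × √(2/337) = 0.12942; 0.51 / 0.12942 = 3.941; Φ(1.981) = 0.9762. Stated: 98%.
- Both, taken as uncorrelated as in 3.8: 0.9835 × 0.9762 = 0.960. Stated: 96%.

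The stated power therefore describes the untransformed analysis. Fixing that scale needs no change in sample size.

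**Step 2: what a transformation does to the target.** For a non-linear function g, the between-arm difference in the mean of g(change) does not convert back into a difference in mean change. A rank analysis compares orderings. Neither 0.6 nor 0.51 episodes per day can be read on such a scale.

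Nor does the clause point to one method. Change is post-baseline minus baseline (SAP 6.3), so it is signed. In the simulated data of Step 3, 22.6% of UUI-like and 27.7% of micturition-like patients had zero or positive change, leaving 77.4% and 72.3% negative. A plain log or square root is undefined for those negative values. A shift constant, a sign-preserving function or ranks would be needed, and the SAP chooses none of them.

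**Step 3: upper bound on type I error, scale chosen by p-value.** The distributions are assumptions; none comes from the SAP. There were 10,000 null trials per endpoint, each analysed by baseline-adjusted ANCOVA at Week 12.

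- UUI-like: baseline 1 + gamma(1.2, scale 2.0). Week 12 is a seven-day Poisson count, with the baseline rate multiplied by a lognormal(−0.7, 0.9) factor.
- Micturition-like: baseline 8 + gamma(2.0, scale 1.7). Change is −1.3 plus normal error with SD 2.2, and Week 12 is floored at 2.

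| | UUI-like, 337 per arm | Micturition-like, 450 per arm |
|---|---|---|
| Raw | 4.98% | 4.88% |
| Signed cube root | 5.26% | 4.96% |
| Rank | 4.94% | 4.90% |
| Signed log | 5.24% | 4.93% |
| Any of the four, two-sided | 9.26% | 7.36% |
| Raw, favourable direction | 2.27% | 2.40% |
| Any of the four, favourable direction | 4.49% | 3.65% |

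Each scale holds its level when fixed in advance. The simulated SD of change was 3.40 for UUI, wider than the SAP's 1.68, and 2.19 for micturitions, close to 2.20.

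Two further UUI-like null simulations (337 per arm) gave similar results:

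- SD about 1.9, residual skew 2.8, 6,000 trials: raw 5.3%; best of raw, shifted log and rank 9.2%; adding cube root 10.5%.
- Strongly skewed data, 4,000 trials: 5.1%, 9.0% and 10.9% for the same three choices.

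**Step 4: scale chosen by residual fit, which is closer to the rule as written.** Using skewed UUI-like null data and taking the scale with the straightest normal probability plot:

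- Among raw, shifted log, shifted square root and cube root: 5.1%, 4.5% and 5.1% in three scenarios of 4,000 trials.
- With rank in place of square root: 4.8% and 5.0%.
- In one further check: 5.4%, against 10.1% when the scale was picked by p-value.

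**Step 5: effect of requiring both endpoints.** Take the worst case of Step 3 and uncorrelated endpoints.

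- Both nulls true: 0.0736 × 0.0926 = 0.0068, well below 0.05.
- Micturitions with its planned effect, UUI null: 0.9835 × 0.0926 = 0.091, against 0.9835 × 0.0498 = 0.049 with the raw scale fixed. In the favourable direction only, 0.9835 × 0.0449 = 0.044 against 0.9835 × 0.0227 = 0.022.

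**The case against.** A reader might infer that the plan lets the primary type I error rise to 9% to 11%. The documents do not support that. The trigger is the look of the residuals, not the treatment p-value, and it is reserved for gross departures. When the scale follows residual fit, error stays near 5% (Step 4). The higher figures need the rule to be misused, depend on assumed distributions, and are two-sided per endpoint. In the favourable direction alone the worst case stays below 5%, and the requirement that both endpoints succeed cuts the joint rate further when both nulls are true. It gives little protection when one effect is real, as Step 5 shows.

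A reader might also infer that the choice can only be made after unblinding. That is not stated. Pooled residuals from a model without treatment could be inspected blinded. SAP 3.9 places a data review before unblinding but neither provides for nor excludes such a check. What stands is that the visible text provides no blinded check, the model as written includes treatment, and analysts receive the unblinded database for the analysis.

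The clause may also never be invoked, since the outcome averages at least 4 diary days and the raw test is robust at these sample sizes. That is a fair limit on the practical effect, but it equally shows that the clause is not needed for validity.

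The text of 8.1.1.2 is blacked out and 8.1.2.2 shows no text in the public copy. A supportive analysis for non-normality may already be there. It would not settle the primary scale left open in 8.1.1.1 and 8.1.2.1.

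**Conclusion.** The point holds, as an inexpensive improvement rather than a flaw that undermines the trial. SAP 8.1.1.1 and 8.1.2.1 require an unnamed transformation on an undefined visual trigger. Following them would replace the raw-scale mean difference that SAP 3.8 hypothesises and powers. This part rests on the text alone and needs no simulation.

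The error-rate part is secondary: about 5% if the scale is chosen by residual fit, and about 7% to 11% two-sided per endpoint only if it is chosen by p-value. The second range is an upper bound, resting on assumed null distributions and on three or four assumed candidate scales. With the raw scale fixed, the simulated level was 4.9% to 5.3% and the stated power stands at 98.3%, 97.6% and 96.0% jointly.

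**What to change.** Delete the transformation sentence in 8.1.1.1 and 8.1.2.1. State that the untransformed MMRM is the primary analysis whatever the residual plots show, and that this also holds for the key secondary endpoints that refer back to 8.1.1.1. Keep the residual inspection as a diagnostic. If the residuals are grossly non-normal, report one supportive analysis named in advance, for example a rank-based ANCOVA at Week 12, that does not replace the primary. If the redacted text already contains such an analysis, a cross-reference is enough.

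Naming one transformation, or settling the scale at a blinded review, would also close the open choice. Either would still move the primary test off the scale of the hypotheses if the clause were used, so keeping the raw scale is the better remedy.

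The cost is wording in two sections, one extra table and a possible small loss of efficiency under strong skew. Sample size is unaffected.
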